### 1.1.1 Flow diagram summary of the trial

### 1.1.2 Brief description of the sequence and duration of all trial periods

There will be an enrollment period lasting up to 60 days, a treatment period consisting of 4 infusions over 10 days, and a follow-up period of approximately 50 weeks (Visit 6 [Week 2] through Visit 11 [Week 52]). The subjects are expected to be in the trial for approximately 60 weeks (14 months). See Section 1.1.1 for a summary of the trial as a flow diagram and Section 1.6 for a tabular schedule of events.

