### 9.3.2 Subject discontinuation from the IMP

Discontinuation of IMP applies only to the treatment period. Subjects who are discontinued from IMP should not be discontinued from the trial except for the reasons indicated in [Table 1](#). Subjects who are discontinued from IMP should be encouraged to remain in the trial for their own safety and for the integrity of the trial.

Subjects must be evaluated prior to each infusion of IMP. The investigator must permanently or temporarily discontinue treatment with IMP for any reasons listed in [Table 2](#). The investigator may decide to temporarily discontinue a subject from receiving IMP for other reasons if further assessments may be helpful to assure safety of the subject. The investigator may also choose to permanently discontinue a subject from treatment if they believe that continued exposure of the subject to neridronic acid may pose an undue risk to the subject, e.g., due to particular adverse events or due to deterioration in the subject's health for reasons related or unrelated to the treatment.

In situations where treatment is temporarily discontinued, the treatment period may be extended to a maximum of 21 days (i.e., Visit 5 should occur no later than 21 days after Visit 2). Visit 6 will be scheduled to occur 4 days ( $\pm 2$  days) after Visit 5, but all subsequent visits should occur as originally scheduled relative to Visit 2 (e.g., Visit 7 will be 42 days [6 weeks] after Visit 2). No more than 4 infusions may be administered during the treatment period, and a minimum of 48 hours between any 2 infusions is required.

Table 2: Reasons for permanent and temporary discontinuation of subjects from IMP

Reason	Discontinuation from IMP	
	Permanent	Temporary
Symptomatic hypocalcemia.	X	
Serum calcium <7.8 mg/dL (<1.95 mmol/L). The subject may resume treatment following investigator assessment and a repeat serum calcium value above this limit (albumin-corrected serum calcium should be considered if serum albumin is below 3.5 g/dL).		X
Clinical signs of dehydration (e.g., dizziness, palpitations, confusion).		X
Evidence suggestive of a possible change in renal function:		

 
A persistent <math>\geq 25\%</math> decrease from baseline (last value observed prior to treatment) in the eGFR, based on repeated central laboratory results from blood samples obtained at least 1 week apart a.
 
	X	

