#### **11.1.2 Treatment period**

The target dosing schedule is Day 1, Day 4, Day 7, and Day 10. Flexibility of  $\pm 1$  day is allowed for Day 4, Day 7, and Day 10, keeping the overall duration of the infusions within the 10-day period (11 days if Day 10 +1 day). A minimum period of 48 hours is required between infusions.

Central safety laboratory data from the previous visit, in particular eGFR, must be evaluated prior to each infusion.

See Section 9.3.2 for details of temporary suspension of IMP.

Due to the number of procedures and assessments at the infusion visits, subjects should arrive at the site at least 1 hour to 2 hours prior to the start of the infusion; subjects will remain at the center for 1 hour after the end of the infusion for evaluation.

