**8.2.2 Further definitions**

Term	Definition
Baseline	
For this single-arm non-randomized trial, baseline is the last observation (scheduled or unscheduled) before first IMP administration, unless specified otherwise. In general, baseline is the value recorded at Visit 2.
 
For physical examinations, a general assessment will be done at Visit 1, and at all subsequent visits (scheduled or unscheduled) the change compared to the previous visit will be assessed.
 
For bone imaging assessments, a separate baseline visit must be scheduled during the enrollment period for subjects undergoing bone densitometry and magnetic resonance imaging procedures.

Early termination visit	Subjects who discontinue the follow-up period before their last planned visit should undergo an Early Termination Visit with procedures identical to Visit 11. If a subject discontinues then, the data recorded under Visit 11 in the eCRF are treated as data belonging to the Early Termination Visit.
Follow-up period	The follow-up period starts after the treatment period and ends at Visit 11.
Follow-up completers	Subjects completing Visit 11 in the follow-up period. Intermittent missed visits in the follow-up period are allowed and do not affect the follow-up completion status.
Investigational Medicinal Products (IMP)	Neridronic acid in the form of sodium neridronate hemi hydrate 108 mg for intravenous infusion (equivalent to 100 mg neridronic acid) supplied in 8 mL of excipients. The full contents of a single ampule or vial (8 mL) will be diluted in 500 mL normal saline and administered by slow intravenous infusion (240 minutes [maximum 260 minutes]) at Visit 2, Visit 3, Visit 4 and Visit 5, resulting in a total dose of neridronic acid 400 mg.
On-treatment-period	For the purpose of this trial, the on-treatment period starts at the first IMP administration (included) and continues until the date (included) when the subject leaves the trial, i.e., at Visit 11 for trial completers, and otherwise at the Early Termination Visit for discontinued subjects. This is based on the persistence in bone and potentially prolonged effect of neridronic acid.

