Pooling of sites	
Individual sites will be combined to achieve pooled sites of similar size and with a sufficient number of subjects. Sites will be pooled by geographical region. The majority of sites are located in the United States of America (USA). Sites in the USA will be pooled in 4 regions based on United States (US) states:
 
 
• US North East: Connecticut (CT), Delaware (DE), Illinois (IL), Indiana (IN), Maine (ME), Maryland (MD), Massachusetts (MA), Michigan (MI), New Hampshire (NH), New Jersey (NJ), New York (NY), Ohio (OH), Pennsylvania (PA), Rhode Island (RI), Vermont (VT), and Washington D.C. (DC).
 
• US South East: Alabama (AL), Florida (FL), Georgia (GA), Kentucky (KY), North Carolina (NC), South Carolina (SC), Tennessee (TN), Virginia (VA), and West Virginia (WV).
 
• US Midwest: Arkansas (AR), Colorado (CO), Iowa (IA), Kansas (KS), Louisiana (LA), Minnesota (MN), Mississippi (MS), Missouri (MO), Montana (MT), Nebraska (NE), New Mexico (NM), North Dakota (ND), Oklahoma (OK), South Dakota (SD), Texas (TX), Wisconsin (WI), and Wyoming (WY).
 
• US West: Alaska (AK), Arizona (AZ), California (CA), Hawaii (HI), Idaho (ID), Nevada (NV), Oregon (OR), Utah (UT), and Washington (WA).
 
 
The sites in Europe will be pooled in one region, European Union (EU).

Pre-treatment-period	Before first IMP administration (excluded), i.e., the period between signature of the informed consent form and first administration of IMP.

Term	Definition
Subjects discontinued from treatment	Subjects permanently discontinued from IMP, i.e., subjects who stopped treatment prior to, or at any time during Visit 2, 3, 4, or 5.
Treated subjects	Subjects with at least 1 administration of IMP, including partial infusions.
Treatment period	The treatment period includes the four infusion visits starting at Visit 2 up to Visit 5. If a subject is permanently discontinued from treatment, the treatment period ends at the visit of the last infusion.
Treatment completers	Treated subjects who completed IMP administration according to the protocol, i.e., subjects who received the full dose of all 4 planned infusions of IMP. Treatment completers form the Treatment Completers Set defined below.
Trial completers	All subjects completing Visit 11 according to the protocol.

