## 10.2 Subject discontinuations

Discontinuations from the trial and from IMP will be presented for allocated subjects overall, and per country.

Reasons for discontinuations from the trial and from IMP will be presented for:

- Subjects allocated and discontinued from the trial
- Subjects allocated and discontinued IMP intake.
- Subjects allocated and discontinued from the trial per trial phase, i.e., during the treatment period, and during the follow-up period

Percentage denominator will be the number of subjects discontinuing.

The details for “other reasons” will be presented in a listing, if applicable.

If more than 10% of the allocated subjects discontinue the trial/IMP the distribution of the time to discontinuation from trial/IMP will be summarized using time-to-event methods. Time will be days until discontinuation. The time to discontinuation from the trial will be censored at the subject’s last planned visit, i.e., Visit 11. The time to discontinuation from IMP will be censored at the last planned infusion visit (Visit 5) or at the early termination visit in case of premature discontinuation from the trial, whichever occurs first.

All data will be presented in a subject data listing sorted by site.

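### Read literally, the SAP's period definitions count a subject who leaves the trial between infusions as a follow-up discontinuation, and the SAP is inconsistent about these subjects

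*SAP*

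**What the plan says.** SAP 8.2.2 gives a base rule: "The treatment period includes the four infusion visits starting at Visit 2 up to Visit 5". It then shortens the period for some subjects: "If a subject is permanently discontinued from treatment, the treatment period ends at the visit of the last infusion". The same table describes the group to which the shorter period applies: "Subjects permanently discontinued from IMP, i.e., subjects who stopped treatment prior to, or at any time during Visit 2, 3, 4, or 5". On the next period it says: "The follow-up period starts after the treatment period and ends at Visit 11".

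These periods feed the disposition tables. SAP 10.1 lists, and SAP 10.2 gives reasons for: "Subjects allocated and discontinued from the trial per trial phase, i.e., during the treatment period, and during the follow-up period".

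Protocol 1.1.2 describes a treatment period of four infusions over 10 days, followed by "a follow-up period of approximately 50 weeks (Visit 6 [Week 2] through Visit 11 [Week 52"]). SAP 5.1 repeats that description. SAP 7.1, which lists changes from the protocol, does not mention a different start of follow-up.

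SAP 10.2 also says how time to IMP discontinuation is censored: at Visit 5, or at the early termination visit if the subject leaves the trial prematurely, whichever comes first.

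**The concern.** The shortening rule suits a subject who stops IMP and stays in the trial. Protocol 9.3.3.2 sends that subject to Visit 6 about 4 days after the last infusion. The rule fits poorly when leaving the trial is itself what ended dosing. Such a subject has stopped treatment before Visit 5, so the treatment period closes retrospectively at the last infusion visit, and the exit falls in follow-up even though no follow-up visit was reached.

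Safety and tolerability are the primary objective, and whether subjects leave during dosing or in the following year is basic tolerability information. The time-to-discontinuation analysis in SAP 10.2 runs only if more than 10% of allocated subjects discontinue. Below that threshold, the per-phase split is the planned disposition summary that shows when subjects left the trial. Percentages for reasons use the number discontinuing as denominator, so a few subjects in the wrong row can be visible.

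**Working it through.** The plan states no figure for this point, so there is nothing to reproduce. The check applies the SAP definitions literally to each possible exit time after the first infusion.

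**Inputs**
- Schedule (Protocol 11.1.2): "The target dosing schedule is Day 1, Day 4, Day 7, and Day 10".
- Longest dosing phase (Protocol 9.3.2): "the treatment period may be extended to a maximum of 21 days (i.e., Visit 5 should occur no later than 21 days after Visit 2").
- Period definitions and table rows: SAP 8.2.2, 10.1 and 10.2, as quoted above.

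**Target schedule, literal reading**

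| Exit from the trial | Last infusion visit | Row in SAP 10.1/10.2 |
|---|---|---|
| Day 1, after infusion start | Visit 2 (Day 1) | treatment |
| Days 2, 3; Day 4 before infusion | Visit 2 (Day 1) | follow-up |
| Day 4, after infusion start | Visit 3 (Day 4) | treatment |
| Days 5, 6; Day 7 before infusion | Visit 3 (Day 4) | follow-up |
| Day 7, after infusion start | Visit 4 (Day 7) | treatment |
| Days 8, 9; Day 10 before infusion | Visit 4 (Day 7) | follow-up |

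**Share of days that always give follow-up**
- Target schedule: Days 1 to 9 contain 3 infusion days, so 9 − 3 = 6 days, and 6/9 = 67%.
- Extended schedule, assumed to be Days 1, 4, 7 and 22: Days 1 to 21 contain 3 infusion days, so 21 − 3 = 18 days, and 18/21 = 86%.

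These are shares of days, not of subjects. Exits may cluster on infusion days. A subject lost to follow-up whose last contact was an infusion visit may also be dated to that visit.

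**The competing reading.** If trial exit is not an IMP discontinuation, as the censoring sentence in SAP 10.2 implies, the shortening rule is not triggered. Visit 2 to Visit 5 then applies, and every exit in the table falls in the treatment period. For k subjects who leave between infusions, or before that day's infusion, the treatment row therefore includes either k or 0 of them. As an illustration with assumed values, k = 1, 3 or 6 out of about 290 subjects is 0.3%, 1.0% or 2.1%.

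**Two related gaps**
- SAP 20.1.1.14 assigns early termination data to the next scheduled visit when the last visit lies between Visit 2 and Visit 7. The Day 3 leaver can then have data at Visit 3, an infusion visit, while being counted as a follow-up loss.
- The tables cover allocated subjects. One who was allocated but never infused has no last infusion, so the phase is undefined.

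**The case against.** The strongest counter-argument is the censoring sentence. If SAP 10.2 regards trial exit during dosing as censoring for IMP discontinuation, these subjects are not permanently discontinued from treatment and keep the full Visit 2 to Visit 5 period. This carries weight: it shows that the literal reading is not the only one. But the sentence concerns a time-to-event analysis and does not redefine the phases, while the definition in SAP 8.2.2 of subjects discontinued from treatment is broad enough to include these subjects. The result is two rules giving different counts.

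A second argument is that early losses are visible elsewhere: IMP discontinuations with reasons, the Treatment Completers Set, the count of subjects with four infusions, dose and compliance by visit, TEAEs leading to discontinuation, and listings. This stands, and it limits the consequence.

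A reader might infer that almost everyone who leaves during dosing is misfiled, so that the treatment-phase row is near zero by construction. The documents do not support that. Exits on an infusion day after the infusion has started are counted correctly, the alternative reading would count all of them correctly, and no exit-time distribution is given. A reader might also infer that safety results are distorted. They are not: the on-treatment period runs from first IMP until the subject leaves the trial, and SAP 20.1.6.1 does not assign adverse events to trial phases.

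**Conclusion.** The point holds in a limited form. On the literal definitions, a trial exit between infusions, or on an infusion day before that day's infusion, is counted as a follow-up discontinuation when the exit is what ended dosing. This conflicts with the start of follow-up at Visit 6 in Protocol 1.1.2 and SAP 5.1, and SAP 10.2 is inconsistent on whether such an exit is an IMP discontinuation.

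The effect is confined to the per-phase discontinuation counts and reasons. The number of subjects cannot be derived from the documents. The 67% and 86% describe calendar days, the second on an assumed extended schedule, and the values of k are assumptions. The conclusion itself rests only on the wording of the definitions.

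**What to change.** Add a phase rule to the SAP for the disposition tables only:

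- **Treatment period:** the subject was allocated, had not completed the fourth infusion, and left the trial on or before the actual or scheduled Visit 5 date with no Visit 6 or later visit performed. This includes allocated subjects who were never infused.
- **Follow-up period:** all other trial discontinuations. This includes subjects who stopped IMP, stayed in the trial and left later, even if they missed Visit 6.

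Both the date limit and the visit condition are needed. Without the date limit, a subject who stops IMP after Day 1, misses Visit 6 and withdraws at Week 26 would be placed in the treatment period.

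Keep the shortening sentence in SAP 8.2.2 for subjects who stop IMP but remain in the trial. Align the censoring text in SAP 10.2 with this rule, so that the SAP says in one way whether a trial exit before the fourth infusion is an IMP discontinuation.

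The cost is SAP wording and one derivation from dates already collected. Total discontinuations do not change.

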## 9 SUBJECT POPULATIONS

### 9.1 Enrolled Set

The Enrolled Set includes all subjects who signed the informed consent form.

### 9.2 Allocated Set

The Allocated Set includes all subjects who are allocated to treatment.

### 9.3 Safety Set

The Safety Set includes all subjects with at least 1 IMP administration, including any partial infusion. The Safety Set will be the primary analysis set in this trial.

Analysis on the SAF will be conducted on the actual treatment received.

### 9.4 Full Analysis Set

The Full Analysis Set includes all subjects allocated with at least 1 IMP administration, including any partial infusion. In this trial, the Full Analysis Set coincides with the Safety Set.

Analysis on the FAS will be conducted according to the allocated treatment. In this single-arm trial, the allocated treatment is the same as the actual treatment.

### 9.5 Treatment Completers Set

The Treatment Completers Set (TCS) includes all treated subjects who completed IMP administration according to the protocol, i.e., subjects who received the full dose of all 4 planned infusions of IMP.

### 9.6 Pharmacodynamic Set

The Pharmacodynamic Set (PD Set) includes all treated subjects with at least 1 non-missing value for at least 1 of the bone turnover markers will be included in the Pharmacodynamic Set.

## **9.7 Bone Biopsy Set**

All subjects with at least 1 bone biopsy evaluable for histology or histomorphometry will be included in the Bone Biopsy Set.

## **9.8 Bone Imaging Set**

All subjects with at least 1 DXA or MRI image evaluable for BMD (DXA) or bone marrow lesion volume (MRI) will be included in the Bone Imaging Set.

# **10 DISPOSITION**

## **10.1 Subject disposition**

All presentations for subject disposition will be overall, i.e., for the single treatment group neridronic acid 400 mg.

For describing the subject disposition, the following populations will be summarized:

- Subjects enrolled.
- Subjects enrolled but not allocated and reason for non-allocation.
- Subjects allocated.
- Safety Set.
- Full Analysis Set.
- Treatment Completers Set (i.e., Treatment completers).
- Pharmacodynamic Set.
- Bone Biopsy Set.
- Bone Imaging Set.
- Trial completers.
- Follow-up completers.
- Subjects allocated and discontinued from the trial.
- Subjects allocated and discontinued from the trial per trial phase, i.e., during the treatment period, and during the follow-up period.
- Subjects who received 4 infusions, including partial infusions.
- Subjects allocated and discontinued IMP intake.
- Subjects allocated and discontinued IMP intake due to deterioration in renal function.

For subjects enrolled but not allocated and for the reasons for not being allocated, the percentage denominator will be the number of enrolled subjects. For all other calculations, the percentage denominator will be the number of allocated subjects.

In addition, an overview table will be prepared presenting the number of subjects enrolled, allocated, in the SAF, in the FAS, in the TCS, PD Set, Bone Biopsy Set, and Bone Imaging Set if applicable per country. Percentage calculation will be done in two ways:

- The denominator will be the number of all allocated subjects.
- The denominator will be the number of allocated subjects in the respective country.

Reasons for exclusion from the analysis populations will be summarized. The percentage denominator will be the number of subjects allocated.

## 10.2 Subject discontinuations

Discontinuations from the trial and from IMP will be presented for allocated subjects overall, and per country.

Reasons for discontinuations from the trial and from IMP will be presented for:

- Subjects allocated and discontinued from the trial
- Subjects allocated and discontinued IMP intake.
- Subjects allocated and discontinued from the trial per trial phase, i.e., during the treatment period, and during the follow-up period

Percentage denominator will be the number of subjects discontinuing.

The details for “other reasons” will be presented in a listing, if applicable.

If more than 10% of the allocated subjects discontinue the trial/IMP the distribution of the time to discontinuation from trial/IMP will be summarized using time-to-event methods. Time will be days until discontinuation. The time to discontinuation from the trial will be censored at the subject’s last planned visit, i.e., Visit 11. The time to discontinuation from IMP will be censored at the last planned infusion visit (Visit 5) or at the early termination visit in case of premature discontinuation from the trial, whichever occurs first.

All data will be presented in a subject data listing sorted by site.

## 10.3 Protocol deviations

Major protocol deviations will be summarized overall, and by pooled site and site based on the SAF and will be grouped into different categories such as:

Category code	Category definition
PD01	Violation of inclusion/ exclusion criteria
PD02	Time schedule deviations
PD03	Non-compliance regarding intake of IMP or rescue medication
PD04	Inappropriate intake of concomitant medication
PD05	Missing essential data
PD06	Subject not discontinued as per protocol
PD07	Other protocol deviations
NC08	Other GxP non-compliance

Major protocol deviations will be presented in a subject data listing sorted by treatment, pooled site, and site.

The list of definitions of protocol deviations (SDN-NONCOMP-DEF-01) may be updated during the trial and will be finalized before database lock. Multiple deviations can occur in the same subject and thus a subject can be counted in more than 1 deviation category.

## **11 DEMOGRAPHICS AND OTHER BASELINE CHARACTERISTICS**

Subject demographics and baseline characteristics will be summarized descriptively overall, i.e., for the single treatment group neridronic acid 400 mg, for the SAF.

This also applies to the summaries of medical history including dental history and CRPS history, and the summaries of prior and concomitant medication or therapy.

### **11.1 Subject demographics**

Subject demographics are age [years], height [m], sex, race, ethnicity, and age group. Age group will be derived. Age groups will be <18 years, ≥18 years and <65 years, ≥65 years and <85 years, and ≥85 years.

All demographic data will be presented in a subject data listing.

The continuous variables age and height will be descriptively summarized. Sex, race, ethnicity, and age group will be summarized as categorical variables.

Remark: Weight is recorded repeatedly together with the vital sign parameters. Therefore, weight and body mass index (BMI) are described in Section [15.2.2](#).

